Appendix 1. Question guide

Understanding the patient experience of day-case bladder tumour resection, and prostate resection or enucleation: Qualitative patient interviews.

[Question guide / script.](#)

Introduction

“Thank you for agreeing to this interview. It is kind of you to offer your time for it. We have asked you to talk to us because you recently had an operation involving your [bladder/prostate/kidney stones], and you went home on the same day as the operation. We want to understand what this was like for you.

We will record the interview so that we can re-visit it later, and we will transcribe the interview in to text for analysis. The transcript will be anonymised. You can pause or end the interview at any time and there is no obligation to answer any of the questions.

Before we start, do you have any questions?

Are you happy for me to start recording and begin the interview?”

Opening questions (4 questions)

“To start off, can you tell me about the operation that you recently had?”

Day-case endourology questions (9 questions)

“Tell me what you understand by the term “day-case surgery.”

[If 23 hour stay is included in answer, clarify that for this study we will specifically be considering instances where the patient leaves the hospital on the same day as the surgery, before midnight.]

“How did you feel knowing that you were going to go home on the same day?”

“Can you tell me about any particular advantages or disadvantages to going home on the same day after your operation?”

“Tell me about the information you received about your operation.”

“Can you tell me what it was like going home on the same day as your operation?”

“Tell me about your experience of travelling home after your operation.”

“Were you able to manage at home after your operation?”

“If you or a member of family needed to have this operation, would you be happy to have it as a day-case?”

“Have you had this operation before?”

“Is there anything else that you would like to tell us based on your experience?”

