Interviewees will be asked to situate themselves in a quiet room on their own and free from distraction for remote interviews, and the interviewer will also locate himself in a distraction-free environment. Open questions will be asked about the patient's experience of day-case surgery, with the nature of follow up questions depending on the initial answers. The feasibility of the question guide will be tested during an internal pilot study performed at the Royal Devon and Exeter Hospital (sponsor site).

Timing:

Within the study timeline, interviews will be arranged at a time and date that is convenient for the interviewee.

Questions:

A semi-structured interview format will be utilised. This involves using a pre-designed question guide, with themes explored in greater depth depending on the interviewee's answers. The questions are designed to signpost areas of fundamental importance, as established following consultation with clinicians, academics, and a patient and public involvement group. The study question guide is included in Appendix 2.

Descriptive data collection:

A limited set of descriptive data will be collected alongside the interviews. This will describe the following; participant age, sex, ethnicity, hospital, region, operation experienced, comorbidities, disabilities, and whether they require social care.

Interview transcription:

For interviews conducted using Microsoft Teams, the integrated recording and transcription function will be used. For interviews recorded using the phone, the Voice Memos iPhone app will be used to record audio. Third party transcription service will be utilised to transcribe interview audio into text (Bristol Transcription and Translation Service). They are an ISO:9001 (quality) and ISO: 27001 (information security) and Cyber Essentials certified business. I attach a document describing their data security and management.

The audio files provided to this service will be in a pseudonymised format using a unique study number for each participant. A password protected spreadsheet stored at the sponsor site will contain the complete participant details.

Pilot study:

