Confidentiality: Caldicott principles will be followed throughout and only data directly relevant to the study will be obtained. Personal data will be stored in a link-anonymised format on a password protected encrypted server at the sponsor site and only accessed by trained individuals when necessary. Results will not be presented in a manner that could allow individual participants to be identified by inference. The recorded audio files will be transcribed, and after this point audio and video will be deleted except for the audio file documenting participant consent, which will be stored separately and securely. The transcripts will be stored using the participant's study ID number, with the corresponding personal details held separately.

If at the time of the interview there is a reason to believe that the participant is at risk of serious harm then confidentiality would be broken if necessary in order to ensure the participants safety. This might relate to severe psychological distress or physical symptoms. If at all possible participants would be encouraged to seek medical attention independently.

Scrutiny: Before commencing the interview, it will be re-affirmed to participants that the interview is exploratory in nature, that there are no correct or incorrect answers, and that participants will not be judged nor treated adversely based on their responses to questions.

Sensitive subject matter:

It is possible that patients could find it distressing talking about their experience of their treatment, or their condition which required treatment. Sensitivity and care will be taken during the interview, and the questions have been designed in conjunction with the PPIE group in such a way as to be open and inviting, and not overtly negative or anxiety-provoking.

The PI (interviewer) is an experienced medically trained urology surgery registrar who with extensive experience of providing care for patients who are distressed. This is both in emergency and elective (clinic) based settings, and includes patients who have undergone or are going to undergo surgery. As such, he is adequately resourced to provide appropriate support for patients who become distressed during the course of the interview. In such an event, the following steps will be followed:

1. Stop the interview when signs of distress are identified.
2. Provide time for the participant to be able to think and reflect.

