3. Explore and acknowledge the participant's emotional state. This includes providing an invitation to discuss how they are feeling in further detail. The interview should only be

resumed if the level of distress is low and the participant is judged to be fully able to do so without experiencing excess distress compared with if the interview were stopped.

4. Discuss an action plan with the participant that is suitable to them.
5. Where judged to be necessary based on the assessment of the participant's emotional state, encourage them to contact their GP or mental health/care provider (if applicable)
6. If necessary and with the participant's consent, offer to contact their GP/mental health/care provider on their behalf.
7. Follow the participant up at an appropriately timed later date to establish their wellbeing and support.

Helplines and support services available to patients requiring additional help are as follows:

- The patient's urology care team, with a designated study-specific point of contact at each participant identification centre.
- The patient's GP

Conflicts of interest:

The principle investigator (JJ) will be conducting the interviews. [name] is a urology specialty trainee. No conflicts of interest have been identified and the study is intended to be exploratory, with the aim of uncovering new themes.

Counteracting researcher bias:

The interviews will be conducted by one researcher, who is a urology specialty trainee. In order to ensure that the interviews remain appropriately interviewee-led and that the interviewer is not directing the interview towards specific themes, anonymised audio footage will be reviewed by a trained NIHR qualitative researcher who is providing project supervision. This will be conducted for three initial pilot interviews performed with professionals working at the sponsor site. Subsequent feedback will be provided in interview technique. When performing thematic analysis of transcripts, 20% of transcripts will be analysed by an additional researcher, and a further small subset analysed by a PPIE representative. This is to ensure consistent interpretation of the data and identify any bias.

Adverse event recording and reporting

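### Two scripted interview questions that bear on acceptability are closed and positively framed, and one also merges patient and relative, although the protocol promises open questions

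*Protocol*

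**What the plan says.** The protocol sets a standard for its questions in two places and a related standard for conduct in a third.

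- Interviews: "Open questions will be asked about the patient's experience of day-case surgery, with the nature of follow up questions depending on the initial answers".
- Ethical considerations, under Sensitive subject matter: the questions were designed with the patient and public group "in such a way as to be open and inviting, and not overtly negative or anxiety-provoking".
- Counteracting researcher bias, on how the interviewer behaves: "In order to ensure that the interviews remain appropriately interviewee-led and that the interviewer is not directing the interview towards specific themes", a qualitative researcher reviews pilot audio.

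Under its day-case heading, the Appendix 1 guide scripts "If you or a member of family needed to have this operation, would you be happy to have it as a day-case" and "Were you able to manage at home after your operation".

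The Hypothesis paragraph expects the experience of the three operations to be acceptable within a well-designed pathway. The primary outcome is patients' descriptions of their experience. Themes are to be derived by inductive thematic analysis.

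**The concern.** A closed question that names only the favourable answer makes agreement the easy reply. That matters more here for two reasons.

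- One person, the principal investigator, conducts every interview. Budget Summary and costings describes this person as a research fellow funded by the Getting It Right First Time (GIRFT) urology programme. The Scientific Summary says that programme advocates day-case surgery as the default for bladder tumour resection, and ideally its offer for prostate resection and enucleation.
- Both items touch what the study wants to learn: how patients cope after discharge, and whether they would accept the same pathway again. The background section itself calls the assumed preference for recovery at home untested.

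The item on self or family has a further fault. A bare yes or no cannot be assigned to either person. The sentence also reads awkwardly for the relative, because it is still the interviewee who is asked about having the operation.

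**Working it through.** No sample-size, power or error-rate figure is involved. The check sets the wording of the guide against the protocol's own standard.

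**Step 1: classify the listed questions.** The guide as shown lists 11 questions: 1 opening and 10 day-case.

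- Open in effect: 1 opening + 6 day-case = 7. The six cover the meaning of day-case surgery, feelings about going home the same day, advantages and disadvantages, information received, what going home was like, and the journey.
- Yes/no in form: 11 − 7 = 4. These are managing at home, being happy to have it as a day-case, having had the operation before, and the closing invitation to add anything.

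**Step 2: separate the four yes/no items by what they can do to an answer.**

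- "If you or a member of family needed to have this operation, would you be happy to have it as a day-case": closed, favourable pole only, two people. It bears on acceptability.
- "Were you able to manage at home after your operation": closed, favourable pole only, one person. It bears on acceptability.
- "Have you had this operation before": closed but neutral and factual. It does not lead.
- The closing invitation: a conventional ending. It does not lead.

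Two items therefore combine a closed form with favourable framing on a matter close to the hypothesis. One of the two is also double-barrelled.

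**Step 3: how firm the count is.** The guide's headings announce 4 opening and 9 day-case questions (4 + 9 = 13), while 1 + 10 = 11 appear. Text extraction may have altered the list, so a percentage of closed questions would be unsafe. The finding rests on the wording of the two items, which does not depend on the total.

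**Step 4: do the stated safeguards reach the wording?**

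- The supervisor's audio review covers three pilot interviews with professionals, not patients, and feeds back on technique.
- The pilot study assesses feasibility, with particular attention to interview length and to covering several operation types.
- The second researcher and the patient and public representative analyse a subset of transcripts. That checks interpretation; it cannot recover what a question did not draw out.
- The patient and public group reviewed question order and wording for ambiguity and a non-judgemental tone. The two items stand in the current guide all the same.

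**The case against.** The strongest case against is that this is a semi-structured interview and the guide only marks out areas to cover. Follow-up depends on the answers, and interviews last 45 to 60 minutes. A bare yes can be probed, and the interviewer can ask whether the reply concerns the patient or a relative. Participants are told there are no right or wrong answers. No acceptability rate is planned, so a yes is not an endpoint. Most of this stands, and it is why the effect is likely to be small. It does not remove the departure, because probing depends on the interviewer while the scripted wording is what participants hear first.

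Three stronger readings are tempting, and the documents do not support them.

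- A reader might infer that answers on acceptability are in fact pushed towards agreement. That is a methodological inference; nothing in the protocol shows it.
- A reader might take the question about being happy with day-case surgery as the only one on acceptability. It is not. The questions on feelings beforehand, on what going home was like, and on advantages and disadvantages also bear on it, and all come earlier in the list. The last of these explicitly invites negatives.
- A reader might add "Have you had this operation before" to the fault. It is a neutral filter and a natural lead-in to a comparison. Rewording it would be a matter of style.

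The sentence on interviewee-led conduct also introduces a safeguard on interviewer behaviour. It is better read as context than as a promise about wording that the guide breaks.

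**Conclusion.** The point holds for two items. Both depart from the protocol's promise of open, inviting questions. Both bear on the acceptability hypothesis and may invite agreement, given who asks them. One also mixes two people in a single answer.

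The reach is two scripted lines in a guide planned for at least 15 interviews. The size of any lean towards agreement cannot be derived from the document. The effect on the primary outcome is probably limited, because the other experience questions are open or balanced and probing is planned.

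The conclusion assumes that the two items are put broadly as scripted and that the guide as shown reproduces their wording. It is worth acting on because the change is almost free, not because the findings would otherwise be unsound.

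**What to change.** Reword the two lines in Appendix 1:

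- 'How did you manage at home after your operation?'
- 'If you needed this operation again, how would you feel about going home the same day?', with 'why' kept as a follow-up probe and not built into the question.

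If views about a family member are wanted, ask about them in a separate question.

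The cost is a minor amendment to the guide. Interviews already held with the current wording must be flagged in the analysis. That includes pilot interviews, which the protocol allows into the analysis if the format stays similar.
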